- Sentinel events during the study period related to liver disease, such as cholangitis, ascites, liver transplant listing, liver transplant, and/or death (see Data and Safety Monitoring Plan (DSMP) in Appendix)
- Adverse events in the first 28 days after KP possibly related to NAC, including rash, urticaria, pruritus, tachycardia, hypotension, vomiting, edema, anaphylaxis, and intravenous line issues (see DSMP in Appendix)
- **vi. Dose Modifications** Rules for modifying NAC infusion are as follows, based in part on prior recommendations for NAC therapy in acetaminophen toxicity (also see DSMP in Appendix):³⁵
 - a) Flushing alone, without pruritus, urticaria, or other serious signs
 - No intervention
 - Continue infusion, unless more severe signs develop
 - b) Urticaria
 - Stop infusion
 - Treat immediately with intravenous diphenhydramine (1.25 mg/kg/dose)
 - Restart infusion if symptoms resolve within 1 hour
 - c) Angioedema, hypotension, wheezing
 - Stop infusion
 - Treat with intramuscular epinephrine (0.01 mg/kg/dose), intravenous diphenhydramine (1.25 mg/kg/dose), intravenous glucocorticoid (1 mg/kg/dose), and/or inhaled albuterol, at the discretion of the clinical team
 - Do not restart infusion
 - Continue to follow patients for first two years of life, per study protocol
 - d) Elevation of ALT >700 U/L above baseline, Bc 3x above baseline, TB 3x above baseline, and/or Bc >5 mg/dL above baseline
 - Stop infusion
 - Do not restart infusion
 - Follow patients clinically until elevated ALT/Bc stabilizes/resolves
 - Evaluate for drug-induced liver injury if deemed appropriate by the clinical team, based on FDA recommendations (https://www.fda.gov/downloads/Drugs/.../guidances/UCM174090.pdf)
 - e) If a severe adverse event related to or possibly related to the study drug (see DSMP in Appendix for definition) occurs during the first 7 days of the trial, i.e., during NAC infusion, the infusion will be paused, and an emergency Data Safety Monitoring Board (DSMB) meeting will be convened. If the DSMB deems that causality is unrelated to NAC use, then the trial can be continued.

vii. Concurrent Treatments

a) Standard therapies: All standard therapies will be given during the study period, including ursodeoxycholic acid (20 mg/kg/day), fat-soluble vitamins (AquADEK, 1 ml once or twice daily), and up to one year of post-KP antibiotics (trimethoprim/sulfamethoxazole 5 mg/kg/day). In infants found

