 - Help arrange logistics of DSMB meetings
 - Help prepare materials for DSMB meetings, including minutes of previous meeting, updated AE CRFs, and updated Data CRFs
 - Attend DSMB meetings
- c) Data Safety Monitoring Board
 - Convene via conference call before trial starts, to review protocol and decide on any amendments
 - Meet twice yearly via conference call to review trial progress, examine AE CRFs, examine Data CRFs, determine whether changes in the study are warranted, and determine whether the study should continue
 - Meet on emergency basis as determined by Chairperson
 - (Chairperson) Respond with recommendations within seven days to serious AEs reported by the Principal Investigator

• Adverse Events:

AEs as specified below occurring in the first 28 days after KP will be documented. An AE is defined as any unfavorable and unintended sign, symptom, laboratory finding, or disease temporally associated with the study, whether or not the AE is related to NAC therapy. These include events observed by the study team, reported by parents, and/or detected by laboratory findings. The following targeted AEs are reportable events in this study:

- a) Clinical AEs that are caused by NAC or likely caused by NAC (typically related to hypersensitivity and occurring at start of infusion):
 - Acute flushing
 - Skin erythema
 - Other rash
 - Urticaria

- Hypotension
- Tachycardia
- Edema
- Vomiting
- Wheezing
- Shortness-of-breath
- Bronchospasm
- Anapyhlaxis
- Redness/swelling/pain/bruising at intravenous line site
- Fluid infiltration at intravenous line site
- Vessel thrombosis at intravenous line site
- Infection at intravenous line site
- Loss of intravenous line
- b) Clinical AEs which could occur with BA in the first 28 days after KP, independent of therapy:
 - Increase in AST, ALT, and/or GGT >400 U/L above baseline (pre-KP) values (Note: in BA, baseline liver enzymes are already National Cancer Institute-Common Terminology Criteria for Adverse Events (CTCAE) Grade 3)
 - Increase in Bc >3 mg/dL above baseline (pre-KP) values (Note: in BA, baseline liver enzymes are already National Cancer Institute CTCAE Grade 3)
 - Increase in TB >5 mg/dL above baseline (pre-KP) values (Note: in BA, baseline liver enzymes are already National Cancer Institute **CTCAE** Grade 3)
 - Vomiting with feeds, requiring acid reduction therapy
 - Cholangitis, requiring antibiotic therapy
 - Infection of other etiology requiring treatment
 - Ascites
 - Diarrhea

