 - Complications related to surgery
 - Death

• Serious AEs

Serious AEs, which are a subset of AEs as specified below, occurring at any time during the study period will be documented. In addition, serious AEs will be reported to the DSMB Chairperson within seven days of occurrence with the exception of events related to the management of the natural course of BA (i.e., hospitalizations for cholangitis, poor growth, worsening liver disease after failed KP, etc). After reporting a serious AE, the Principal Investigator and/or study team will receive recommendations about how to proceed with the study within seven days. Serious AEs are those AEs which:

- a) Result in death;
- b) Place the subject at immediate risk of death (does not include AEs which, if more severe, might have caused death);
- c) Require inpatient hospitalization or prolongation of existing hospitalization (with the exception of hospitalizations related to the natural course of BA, such as hospitalizations for cholangitis, poor growth, worsening liver disease after failed KP, etc)
- d) Lead to persistent disability which prevents a subject from conducting normal life functions; or
- e) In the first 28 days after KP, elevation of ALT >700 U/L above baseline, Bc 3x or >5 mg/dL above baseline, and/or TB 3x above baseline.
- Dose Modifications for AEs (including serious AEs) related to NAC infusion (based in part on a previously published protocol)³⁵

- a) Flushing alone, without pruritus, urticaria, or other serious signs
 - No intervention
 - Continue infusion, unless more severe signs develop
- b) Urticaria
 - \circ Stop infusion
 - Treat immediately with intravenous diphenhydramine (1.25 mg/kg/dose)
 - Restart infusion if symptoms resolve within 1 hour
- c) Angioedema, hypotension, wheezing (serious AE)
 - Stop infusion
 - Treat with intramuscular epinephrine (0.01 mg/kg/dose), diphenhydramine (1.25 mg/kg/dose), intravenous glucocorticoid (1 mg/kg/dose), and/or inhaled albuterol, at the discretion of the intensive care unit team
 - Do not restart infusion
 - Continue to follow patients for first two years of life, per study protocol
- d) Elevation of ALT >700 U/L above baseline, Bc 3x or Bc >5 mg/dL above baseline, and/or TB 3x above baseline (serious AE)
 - Stop infusion
 - Do not restart infusion
 - Follow patients clinically until elevated ALT/Bc stabilizes/resolves
 - Evaluate for drug-induced liver injury if deemed appropriate by the clinical team, based on FDA recommendations

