(https://www.fda.gov/downloads/Drugs/.../guidances/UCM174090.pdf)

Reporting

AEs (serious and non-serious) occurring in the first 28 days will be recorded on CRFs and presented to the DSMB at each meeting. In addition, serious AEs occurring at any time during the study period will be reported directly to the Chairperson within seven days of occurrence with the exception of events related to the management of the natural course of BA (i.e., hospitalizations for cholangitis, poor growth, worsening liver disease after failed KP, etc). This reporting schedule is designed to help the DSMB decide whether the trials meets sufficient safety standards to continue. AE CRFs will have describe each AE using the following categories (see sample AE ORF):

- a) Category of AE
 - AEs will be categorized into pre-determined groups, as specified by the CTCAE.
 - These groups include Anemia, Cardiovascular, Congenital, Death, Dermatological, Febrile events, Gastrointestinal, Gynecological, Hematological, Hepatic, Injury, Immunological, Infectious viral, Infectious cholangitis, Infectious surgical, Infectious, Investigation (laboratory results), Metabolic, Miscellaneous, Musculoskeletal, Neoplastic, Neurological, Nutritional, Orthopedic, Pulmonary, Surgical, Urinary, Wound non-infectious, IV Issues
- b) Severity of AE Serious or non-serious
- c) Description of event Concise description of AE, including date occurred
- d) Grading of AE
 - CTCAE grade will be used, in accord with CTCAE Version 5.0
 - If the CTCAE does not have a grading for a particular AE, the severity of the event should be
 reported based on the following (this is independent of an AE designated as serious, which requires
 prompt reporting to the DSMB Chairperson):
 - Grade 1: Asymptomatic or mild symptoms, clinical or diagnostic observations only; intervention not indicated.
 - o Grade 2: Moderate; minimal, local, or noninvasive intervention indicated
 - Grade 3: Severe or medically significant but not immediately life-threatening; hospitalization or prolongation of hospitalization indicated; disabling. (As mentioned above, liver enzymes will be

Grade 3 at baseline, so only AST, ALT, and/or GGT >400 U/L above baseline and/or Bc >3 mg/dL above baseline will be reported as an AE. If this were to occur, the AE would be Grade 3)

- Grade 4: Life-threatening consequences; urgent intervention indicated.
- Grade 5: Death related to AE.
- e) Relationship to NAC

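### Liver-laboratory AE thresholds refer only to the pre-KP value, so a rebound from a post-KP low can miss every targeted laboratory criterion

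*Combined protocol and SAP*

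**What the plan says.** **Laboratory AE thresholds.** DSMP, Adverse Events, sets the window: "AEs as specified below occurring in the first 28 days after KP will be documented". Part b) then gives three laboratory criteria, all against the pre-operative sample:
- "Increase in AST, ALT, and/or GGT >400 U/L above baseline (pre-KP) values"
- "Increase in Bc >3 mg/dL above baseline (pre-KP) values"
- "Increase in TB >5 mg/dL above baseline (pre-KP) values"

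The footnote to the observations table (protocol D.v) places that sample within seven days of KP.

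**Exclusivity and grade.** A parenthesis under Grade 3 in DSMP, Reporting d), explains that liver enzymes are Grade 3 from the start, "so only AST, ALT, and/or GGT >400 U/L above baseline and/or Bc >3 mg/dL above baseline will be reported as an AE". It adds that such an AE would be Grade 3. TB is not named there.

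**Serious AEs.** Criterion e) reads "In the first 28 days after KP, elevation of ALT >700 U/L above baseline, Bc 3x or >5 mg/dL above baseline", plus TB at three times baseline. Baseline is not labelled pre-KP here, but the documents define no other. Protocol D.vi d) uses the same reference.

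**Broader wording elsewhere.** The DSMP's general AE definition takes in unfavorable laboratory findings whether or not they are related to NAC. Protocol E.ii says that every AE, including those found by laboratory tests, is recorded.

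**What needs no baseline.** Treated cholangitis, other treated infection, ascites, surgical complications and death are listed AEs. Serious-AE criteria a) to d) make no comparison with a laboratory baseline.

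**What the DSMB sees.** Data CRFs, with rows for Bc, TB, AST, ALT and GGT, are presented at each meeting.

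**The concern.** Pre-KP bilirubin is the obstructed value that the operation, and by hypothesis NAC, is meant to lower. When it falls, the AE threshold stays where it was. A later deterioration must first regain the whole fall and then add the increment before it counts, so the criterion is least sensitive in the infants who respond best.

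The plan's reason for the restriction is that liver values are already Grade 3 before surgery. That reason lapses once values have fallen, but the rule continues.

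At stake is objective 5, the record of adverse events that may be associated with NAC. The event most likely to be lost is a rebound with no diagnosis attached, such as possible drug injury or unexplained loss of drainage. With 12 to 16 infants planned, one unflagged event is 1/16 = 6.25% to 1/12 = 8.3% of the safety sample. The primary outcome and the two-stage decision rule are not touched.

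**Working it through.** The plan states no figure on this point, so there is none to reproduce. The check is how far a value can climb from its post-KP low without meeting a criterion.

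**Inputs from the documents.** AE increments are +3 mg/dL (Bc), +5 mg/dL (TB) and +400 U/L (AST/ALT/GGT), all above pre-KP. The serious-AE limit for Bc is 3x baseline or more than 5 mg/dL above it, whichever is reached first.

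**Assumed inputs.** The documents give no pre-KP bilirubin distribution and no size of fall. Let B (Bc) or T (TB) be the pre-KP value and N the lowest post-KP value.

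**Formulas for the largest unflagged rise from the low:**
- Bc, AE: (B + 3) − N = (B − N) + 3
- Bc, serious AE: min(3B, B + 5) − N, reading 3x as three times baseline
- TB, AE: (T − N) + 5
- Enzymes, AE: (pre-KP − low) + 400

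In each AE formula the gap is the plan's own increment plus the size of the fall.

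**Illustration, Bc with B = 6, N = 2 mg/dL:**
- AE limit 6 + 3 = 9, so a rise of 9 − 2 = 7 mg/dL (4.5-fold) is not flagged.
- Serious-AE limit min(18, 11) = 11, so a rise of 11 − 2 = 9 mg/dL is not serious by Bc.
- With no fall (N = B = 6), the unflagged rises are 3 and 5 mg/dL.

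**Range for Bc:**

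| Assumed B | Assumed N | Unflagged rise, AE | Unflagged rise, serious AE | Fold at AE limit |
|---|---|---|---|---|
| 4 | 3 | 4 | 6 | 2.3 |
| 6 | 2 | 7 | 9 | 4.5 |
| 8 | 1 | 10 | 12 | 11 |

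Near-normal values are not needed. If Bc only halves (N = B/2), the AE gap is B/2 + 3, or 4.5 mg/dL for B = 3 and 8 mg/dL for B = 10.

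**TB.** With T = 8 and N = 2, the limit is 13 and the unflagged rise is 11 mg/dL. For T = 5 to 12 and N = 1 to 2, it runs from 5 + 5 − 2 = 8 to 12 + 5 − 1 = 16 mg/dL.

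**Does another rule catch it?** Nothing in the documents compares a value with the post-KP low or with the preceding value. The general definition and protocol E.ii could be read to include such a rebound. The limitation to specified, targeted AEs and the word *only* in Reporting d) point the other way. Two staff members could therefore record the same rebound differently.

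**The case against.** A reader might infer that all liver AEs and serious AEs are judged against the pre-KP value, and that a steep rebound is never recorded. The documents do not support that. Rebounds beyond pre-KP +3 (Bc), +5 (TB) or +400 U/L (enzymes) are recorded. Rebounds from treated cholangitis, infection or a surgical complication are captured under those entries, and serious-AE criteria a) to d) apply whatever the baseline, although c) exempts natural-course hospitalizations.

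Nor are the values hidden. In at most 16 planned infants, a fall and rebound could be seen subject by subject on the Data CRF. What stays missing is an AE entry, a grade and an assessment of relation to NAC. Timing also matters: scheduled meetings are required only twice a year, and the seven-day notice covers serious AEs only.

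The size is assumed. The 11-fold end needs Bc to go from 8 to 1 to 11 mg/dL within 28 days with no listed event. Protocol F.i reports a normal Bc within two weeks in only 1/48 (2.1%) of the institution's past patients, so very low early values were rare. That weakens the top of the range, but it says nothing about partial falls or about weeks 3 and 4.

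A pre-treatment reference is a deliberate choice with a stated reason, and AEs are a secondary, descriptive outcome. Both are true. They support keeping the pre-KP rule, not leaving it as the only one.

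**Conclusion.** The point holds in a limited form. The targeted liver-laboratory AE thresholds, and by natural reading serious-AE criterion e), refer only to the pre-KP value. A rebound from a post-KP low that stays within the pre-KP limits and has no listed clinical event meets no targeted laboratory AE criterion. The gap widens by exactly the size of the fall: 7 mg/dL of Bc for an assumed 6 falling to 2, and 4 to 10 mg/dL over assumed pre-KP values of 4 to 8 and lows of 1 to 3. How many infants would be affected cannot be estimated from the documents.

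Reading baseline as pre-KP in criterion e) is an inference. Whether the general AE definition would rescue such a rebound is unresolved, because the passages disagree.

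**What to change.** Recording only:
1. Keep the pre-KP rule. In DSMP Adverse Events b) and Reporting d), add that in the first 28 days a rise of more than 400 U/L (AST/ALT/GGT), 3 mg/dL (Bc) or 5 mg/dL (TB) above the lowest post-KP value so far is also entered on the AE CRF. Flag it as a rebound from the post-KP low and list it separately for the DSMB.
2. State that the automatic Grade 3 label in Reporting d) does not apply to these entries. Otherwise Bc rising from 1 to 4.1 mg/dL in an infant with a pre-KP value of 6 would be Grade 3 while still below baseline.
3. Reconcile protocol E.ii, the general AE definition, the limitation to specified AEs and the *only* sentence in Reporting d), which omits TB.

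No change to the serious-AE or infusion rules is proposed.

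The cost is a few sentences in the DSMP. The values are already on the Data CRF at days 3, 7 and 10 and weeks 2 and 4. The downside is that some natural-course rebounds will be added as AEs; the separate listing keeps them distinguishable.

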Two potentially more serious events have been associated with NAC treatment. The first is severe hyponatremia leading to seizures, after excessive free water was given during intravenous NAC administration in infants.⁴⁰ This occurred partly because NAC therapy for acetaminophen toxicity requires three dose changes in the first five hours, with different NAC concentrations and dilution regimens. To minimize the chances of this occurring, special neonatal dilution instructions are included in the product insert and have been approved by the Food and Drug Administration.¹⁵ The single dilution strategy used in this protocol conforms to these recommendations.

Another potentially serious event that has been reported with oral NAC is paradoxical respiratory adverse drug reactions (ADRs).⁴¹ These events are described as worsening of respiratory disease in patients taking oral overthe-counter NAC (approximately 20-30 mg/kg/day children ages 1 month to 2 years) as a mucolytic agent in the setting of bronchiolitis or pneumonia. NAC is proposed to increase bronchial mucus flow which can overwhelm an infant's ability to spontaneously clear secretions. Fifty-nine cases were identified over a 20 year period in European country. However, in studies of intravenous doses similar to the dose used in this investigation, no paradoxical respiratory ADRs were reported.

A summary of the side-effect profile of intravenous NAC listed on formularies is as follows:

Cardiovascular:	Edema, flushing, tachycardia							
Dermatologic:	Rash, pruritus, urticaria							
Gastrointestinal:	√ausea, vomiting							
Immunologic:	Autoimmune disease							
Miscellaneous:	Anaphylactoid reaction							
Respiratory:	Pharyngitis, rhinorrhea, rhonchi, throat tightness							
Rare but important or life-threatening:	Anaphylaxis, angioedema, bronchospasm, chest tightness, cough, dizziness, dyspnea, hypotension, respiratory distress, stridor, wheezing							

N-Acetylcysteine in BA **I. References**

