 - Related: There is clear evidence that the event is related to the use of study drug (i.e., rash with NAC infusion)
 - Possible: The event cannot be explained by BA, other therapies, or other causes, and these is a plausible temporal relationship between the event and NAC administration
 - Unlikely/Remote: An event for which an alternative explanation is more likely or the temporal relationship to NAC administration does not support a causal relationship
 - Not related: The event can readily be explained by BA, other therapies, or other causes, and therefore the Principal Investigator believes no relationship exists between the event and NAC therapy
- f) Action Taken with Study Drug
 - None: No changes made to NAC administration
 - Discontinued: Study drug was discontinued
- g) Treatment Given for AE A list of any treatments or procedures given for the event.
- h) Outcome of the AE
 - Ongoing: AE persists despite intervention
 - Recovered: Subject recovers completely from AE
 - Change in severity: AE became serious from non-serious or vice versa
 - Unknown
 - Death
- Review of AEs

The DSMB will review all AE CRFs at biannual meetings and review serious AEs if an emergency meeting is called by the DSMB Chair. The DSMB will then decide if the study should be stopped for safety reasons.

• Data Management, Analysis, and Quality Assurance

The DMSB will review enrollment, enrollment targets, and findings recorded for each subject to ensure the validity and integrity of the data. At each DSMB meeting, updated Data CRFs for each subject will also be presented (see sample Data CRF). The DSMB will assure quality assurance, defined as "All those planned and systematic actions that are established to ensure that the trial is performed and the data are generated, documented (recorded), and reported in compliance with Good Clinical Practice (GCP) and the applicable regulatory requirement(s).

Sample Adverse Event (**AE**) Clinical Report Form (**CRF**)

:	Category ¹	Description	SAE?	Grade (CTCAE) ²	Start Date	Outcome ³	End Date	Relationship to NAC ⁴	Action Taken with NAC⁵	Treatment Given	Investigator Initials/Date

Participant ID:

¹ Category of AE:	² Grading of AE (Only If NOT in CTCAE)	³ Outcome of the AE:	⁴ Relationship to NAC:	⁵ Action Taken with NAC:
Anemia, Cardiovascular, Congenital, Death,	Grade 1 – Asymptomatic or mild symptoms; clinical	1 - Ongoing; AE continues	1 - Related	N - none; no changes

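### As defined, *Possible* excludes any event that another cause could explain, so a serious infusion-week event of mixed cause need not trigger the mandatory pause and emergency DSMB meeting

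*Combined protocol and SAP*

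**What the plan says.** The causality scale is in the DSMP, under Reporting, item e (Relationship to NAC). It has four categories:

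- *Related*: "There is clear evidence that the event is related to the use of study drug".
- *Possible*: "The event cannot be explained by BA, other therapies, or other causes", and in addition the timing relative to NAC is plausible.
- *Unlikely/Remote*: "An event for which an alternative explanation is more likely", or the timing does not support causation.
- *Not related*: other causes readily explain the event, and "therefore the Principal Investigator believes no relationship exists between the event and NAC therapy".

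Section D.vi (Dose Modifications), item e, attaches an action to the first two. Its condition begins "If a severe adverse event related to or possibly related to the study drug", with a pointer to the DSMP for the definition. If such an event occurs in the first 7 days, the infusion must be paused and an emergency DSMB meeting held. The item then says: "If the DSMB deems that causality is unrelated to NAC use, then the trial can be continued".

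Section H.iv (Toxicities) names two potentially more serious events linked to NAC. One is "severe hyponatremia leading to seizures, after excessive free water was given during intravenous NAC administration in infants". Hyponatremia is not among the event-specific rules in D.vi items a to d, nor on the DSMP list of targeted adverse events.

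**The concern.** A category called *Possible* should hold the uncertain cases. Here it is a diagnosis of exclusion: one credible alternative is enough to rule it out. After a Kasai operation there is nearly always a candidate, such as the surgery, the underlying disease, intravenous fluids (Section G.ii) or early parenteral nutrition (Section F.i).

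The wording matters because it controls a safety action. Section D.vi item e gives the DSMB a say on causality, but only after the trigger has fired. For a mixed-cause event the site's classification comes first, and the text gives no category that leads to the trigger. There is no control arm in which an excess could show, so case-by-case review carries much of the safety assessment.

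The threshold is also unclear. D.vi item e says *severe* and refers to the DSMP. There, the item headed Severity means serious or non-serious, while the grading item uses *Severe* for Grade 3 and states that grade is independent of seriousness.

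**Working it through.** No plan figure is in dispute. The check applies the four definitions to a serious event in the infusion week with plausible timing, and then applies D.vi item e.

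| Situation | Category on the text | D.vi item e fires? |
|---|---|---|
| Clear evidence for NAC, whatever else is present | Related | Yes |
| No clear evidence; nothing else can explain it | Possible | Yes |
| No clear evidence; another cause can explain it and is more likely | Unlikely/Remote | No |
| No clear evidence; another cause can explain it but is not more likely | None fits cleanly | No |
| Another cause readily explains it and the investigator believes there is no link | Not related | No |

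The fourth row is the gap. The event fails *Related* for want of clear evidence. It fails *Possible* because that definition joins two conditions and the first is not met. It fails *Unlikely/Remote* because the alternative is not more likely and the timing fits. It reaches *Not related* only if the investigator positively believes there is no link.

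The safeguards left for such an event are:

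1. **Event-specific stops (D.vi items b to d).** These cover urticaria; angioedema, hypotension or wheezing; and set rises in ALT or bilirubin. They do not depend on the causality rating, but they do not themselves convene the DSMB and do not cover hyponatremia.
2. **Discretion.** Clinicians may stop the drug, and Section D.viii item b lets investigators remove an infant. Neither is required.
3. **Serious-event notice.** Notice goes to the Chair within 7 days (DSMP, Serious AEs), and a reply is due within 7 days (DSMB Charter, Communication). The outer limit is 7 + 7 = 14 days, against an infusion of 168 h / 24 = 7 days. Events in the natural course of BA are exempt from this notice, so attribution to BA can remove it. The Chair may then call an emergency meeting but need not.

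Hyponatremia shows a second, separate break. The DSMP says the listed targeted events are the reportable ones and describes serious events as a subset of adverse events. Because hyponatremia is not listed, changing *Possible* alone would not make sure that the trigger reaches it.

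**The case against.** The best reply is that a sensible investigator would read the scale as a whole. *Unlikely/Remote* is kept for a more likely alternative and *Not related* for a readily explained event, so a case that fits neither would be called *Possible* in practice. The pointer in D.vi item e may define only the severe event, leaving *possibly related* with its everyday meaning. That may well be how the rule is applied, but it means setting aside an explicit condition in the definition. A safety trigger should not rely on that.

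Other parts of the reply do limit the point:

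- The DSMP lists hypotension, tachycardia, edema, wheezing, bronchospasm, anaphylaxis and line-site events as caused or likely caused by NAC. Recognised reactions are thus largely attributed to NAC already.
- The 7-day limits are maxima, the Chair is the safety officer, and notice of serious events is not filtered by the causality category as such.
- The risk itself is reduced. The reported hyponatremia arose partly from multi-step dilution, and Section H.iv says: "The single dilution strategy used in this protocol conforms to these recommendations". Sodium and weight are followed, and the infusion starts in intensive care, so an event would probably be seen. The gap is in what seeing it must trigger.

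Two stronger readings are tempting and should not be drawn. A reader might infer, from NAC's modest share of daily fluid volume, that other fluids would usually explain a low sodium and so routinely rule out *Possible*. Sodium depends on free water, and the documents give neither total intake nor the tonicity of the other fluids, so this cannot be shown. A reader might also infer that these events would typically wait about six months for a scheduled DSMB meeting. That route is narrow: these infants are inpatients, and an event that prolongs the stay is already serious under the DSMP unless it belongs to the natural course of BA.

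**Conclusion.** The point holds as a defect of wording with a safety consequence. On the text, a serious infusion-week event with a credible non-NAC explanation and no clear evidence for NAC does not set off the mandatory pause and emergency meeting. If no cause is more likely, it has no proper category. The slowest remaining required route takes up to 14 days, twice the length of the infusion.

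The frequency of such events cannot be derived from the documents. Planned exposure is 12 to 16 infants, plus any replacements. The documents do not show that an infant would go unmonitored or that the drug could not be stopped; they show only that stopping and prompt DSMB review would be optional. The conclusion rests on reading *possibly related* in D.vi item e as the DSMP category. If it carries its everyday meaning, the two texts conflict and still need aligning.

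**What to change.** **DSMP, Relationship to NAC.**

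- *Possible*: timing is plausible and NAC cannot be excluded, even if BA, surgery or another therapy could also explain the event.
- *Unlikely/Remote*: an alternative is clearly more likely, or the timing is unsupportive.
- *Not related*: the timing is implausible, or another cause is confirmed.

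**Section D.vi item e.** Replace *severe* with *serious (DSMP definition)*. Extending the trigger to Grade 3 is optional and for the sponsor to decide. The DSMP counts rises above 400 U/L in AST, ALT or GGT, or above 3 mg/dL in conjugated bilirubin (Bc), as Grade 3. That extension could therefore bring in liver-test rises below the stop limits in D.vi item d (ALT above 700 U/L; Bc 3x or above 5 mg/dL; total bilirubin 3x).

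**DSMP targeted events.** Add hyponatremia, since Section H.iv already names it.

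**Cost.** No new data are needed, since sodium is already collected. A few more events will be rated *Possible*, some infusions will be paused for events that prove surgical, and the DSMB will be contacted somewhat more often.

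Waiting for a conference call could exceed the 30-minute interruption limit in Section D.iv item a and the 6-hour tolerance on 168 hours in item b. The amendment should say that a D.vi item e pause is not a protocol deviation and how it counts toward the planned duration. This also bears on the primary analysis, because Section F.ii allows discretionary replacement of infants who do not complete the infusion.
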